3.2.17 Interim analysis

1st Interim analysis

A first interim analysis will be conducted at the cut-off date of 27 September 2019 to inform the design of the chemotherapy combination study which has been added to the investigational plan.

The tables, listings and figures that will be produced for this analysis are flagged “*” in Section 7.2 – List of TFLs.

2nd Interim analysis

A second interim analysis of Part B data will be conducted at the EOCT/EOAC/EW (whichever occurs last) after completion of Cohorts 3 and 6. This will provide confirmation of the peptide dose to allow future studies to be developed. It will also confirm if Cohorts 2 or 7 and 8 will be initiated.

3rd Interim analysis

A third interim analysis, including all dosimetry, safety and efficacy data, will be performed after the EOCT/EOAC/EW (whichever occurs last) when the two study parts are completed.

The interim analyses may be combined based on the overall study status and subject accrual. The final analysis will be performed at the end of the 2-year long-term follow-up period.

Other analyses

In addition, dosimetry evaluation will be performed on an ongoing basis. After the first six subjects included have completed the study Part A (EOCT or Early Withdrawal Visit) an SRC meeting will be held before exposing the remaining subjects to the entire number of planned administrations. Safety data obtained until 8 weeks after the last administration of the 6th subject will be evaluated during this SRC. Prior to Part B, the SRC will review the safety and dosimetry data of the first six subjects included in Part A.

For Part B, a DRB meeting will be held to review the safety and radiation exposure data and decide whether to proceed with the enrolment of the next cohort dose level and the cumulative radioactivity within a cohort. Each dose escalation (both peptide and radioactivity) will be carefully evaluated by a DRB.

In addition, the SRC/DRB can be convened at any time during the trial to discuss potential safety issues. The data set to be reviewed by the SRC/DRB is specified in a specific charter.

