3.2.18 Role of the Safety Review Committee (SRC) – Part A

The SRC will be composed of all Investigators, who have treated at least one subject in the study with study medication, a dosimetry expert evaluating the dosimetry data of the study, an independent hematology expert and at least one Sponsor representative. A specific charter will be developed to define roles and responsibilities, as well as the data set to be reviewed by the SRC.

This study will be performed in two parts:

Part A (15 subjects)

Initially, 6 subjects will be treated. Each patient will receive:

- 3 cycles of 4.5 GBq (target radioactivity of 4.5 GBq±10%) ¹⁷⁷Lu-OPS201 (target dose of 300±50 µg), 8 weeks apart (+2 weeks or plus up to 4 weeks in case of AEs which have not adequately recovered).

A SRC meeting will be held before exposing the remaining 9 subjects of Part A to the entire number of planned administrations. Safety and dosimetry data from the first 6 subjects (data obtained up to 8 weeks after the last administration for each subject) will be evaluated during this SRC.

Dose limiting toxicity (DLT) definition: Investigational medicinal product (IRPP) related AEs with a severity of Grade 3 or higher are considered DLT, with the exception of hair loss, lymphopenia, nonfebrile neutropenia lasting < 4 weeks and thrombocytopenia lasting < 4 weeks.

- If DLTs occur in ≤ 33% of the patients (i.e. ≤ 2 of 6 patients), the remaining 9 patients will continue at the same radioactivity level.

- If DLTs occur in > 33% of the patients (i.e. > 2 of 6 patients), the administered radioactivity will be reduced to a cumulative radioactivity which did not lead to DLT occurrence with this frequency, e.g. the number of administrations will be reduced from 3 to 2.

Part B (up to 40 subjects)

Proceeding to next cohort will be determined by the following DLT rules based on three evaluable subjects:

- If DLTs occur in >33% of the subjects of the cohort, the next cohort will not be initiated.
- If DLTs occur in $\leq 33\%$ and ≥ 2 of the three subjects have cumulative absorbed dose in each target organs exceeding the acceptability limits (1.5 Gy in bone marrow (BM) and 23 Gy in kidney), subjects in the next cohort will receive the same cumulative radioactivity or less than in the preceding cohort.

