- If DLTs occur in $\leq 33\%$ and <2 of the three subjects did not reach the cumulative absorbed dose in each target organs (1.5 Gy in BM and 23 Gy in kidney), the next cohort will be initiated as planned.

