DRB-B	Cohort 3 First three subjects, EOC-2	Start Cohort 4 with 6 GBq?	If >65% DLTs in Cohort 3 then NO to Cohort 4. If >33% and <67% DLTs in Cohort 3 Cycle 2 then wait for three more subjects in Cohort 3 Cycle 2 and re-evaluate. Otherwise start Cohort 4. Cohort 4 will not start recruiting until Cohorts 1, 3 and 6 are fully recruited
DRB-C	Cohort 4 EOC-1	Start Cohort 5? Continue Cohort 4?	If >33% DLTs in Cohort 4 then NO to Cohort 5. If >33% DLTs in Cohort 4 then STOP. Evaluate peptide mass dosing and lesion receptor saturation. Evaluate next cohort to start and activity dosing.
DRB-D	Cohort 6 EOC-3 All subjects Cohort 4 EOC-1	Start Cohort 7?	If >33% DLT in Cohort 6 Cycle 2 NO to Cohort 7 AND If lesion receptor saturation in Cohort 6 Cycle 2, then no to Cohort 7 AND If >33% DLTs and <67% DLTs in Cohort 4 and receptor modelling suggests Cohort 7 mass dose safer, then start Cohort 7, otherwise no.
DRB-E	Cohort 6 EOC-3 All subjects Cohort 5 EOC-1	Start Cohort 8?	If >33% DLT in Cohort 6 Cycle 2 NO to Cohort 8 AND If lesion receptor saturation in Cohort 6 Cycle 2, then no to Cohort 8 AND If >33% DLTs <67% DLTs in Cohort 5 and receptor modelling suggests Cohort 8 mass dose safer, then start Cohort 8, otherwise no.
DRB-F	Cohort 1 EOC-3 and Cohort 3 EOC-3 and Cohort 5 EOC-1	Start Cohort 2?	If mass dose modelling suggest 300 ug is optimal AND If >33% DLTs in Cohort 1, AND If >33% DLTs in Cohort 5 Start Cohort 2

DLT=dose limiting toxicity; DRB=data review board; EOC=end of cycle; GBq=gigabecquerel.

Note: At each DRB, safety data available from all cohorts will be evaluated to inform decision making.

a although the DRBs are written in alphabetical sequence this is not a chronological order; each one will be conducted when data becomes available which is dependent on subject recruitment. An ad-hoc DRB can be called to ensure continuity of dosing. Although three completed subjects are required for each completed cycle for evaluation, all available subject data in that cohort will be used (e.g. If five subjects are enrolled and all five complete the end of a cycle prior to the DRB, then all five sets of data will be evaluated).

This cumulative activity in the cohort being evaluated will be determined by the following DLT rules:

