- If, in the preceding cohort after the third administration of ¹⁷⁷Lu-OPS201, DLTs occur in >33% of three subjects (i.e. >1 out of the three to five subjects), the activity for the next cohort will be reduced to a cumulative administered activity which did not lead to DLT occurrence with this frequency.
- If, in the preceding cohort after the third administration of 6GBq ¹⁷⁷Lu-OPS201, DLTs occur in ≤33% of three subjects and ≥2 of the three subjects have a cumulative absorbed

dose in each target organ exceeding the acceptability limits (1.5 Gy in BM and 23 Gy in kidney), subjects in the next cohort will receive the same cumulative activity or less than in the preceding cohort.

- If, in the preceding cohort after the third administration of 6GBq ¹⁷⁷Lu-OPS201, DLTs occur in ≤33% of the three subjects and less than two of the three subjects did not reach the cumulative absorbed dose in each target organ (1.5 Gy in BM and 23 Gy in kidney), the activity in the next cohort will be escalated up to 7.4 GBq per administration, as detailed in the table above

Data Review Board

- the DRB will consist of a team of “permanent” decision makers (the core team);
- principal investigators may participate, present and listen in;
- all final decisions will be made by the core team;
- the number of DRB meetings may change as needed and can be called upon rapidly if there is a safety issue of concern in a cohort;
- the aim is to have all meetings via conference call, but if the timing does not allow for this, then it can be conducted via email exchange or two conference calls with split attendees;
- a DRB charter will be developed with further details.

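### After DLTs in more than 33% of a Part B cohort, SAP 3.2.18 bars the next cohort, SAP 3.2.19 only lowers its activity, and for Cohort 2 the DRB-F row says start

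*SAP*

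**What the plan says.** The Part B escalation rules appear twice in the SAP.

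- **SAP 3.2.18**, under the heading for the Part A committee, gives three branches based on three evaluable subjects. Above 33% DLTs: "If DLTs occur in >33% of the subjects of the cohort, the next cohort will not be initiated". At or below 33% with organ-dose limits exceeded in at least two of three: "subjects in the next cohort will receive the same cumulative radioactivity or less than in the preceding cohort". Otherwise: "the next cohort will be initiated as planned". Protocol 3.8 and the Synopsis dose escalation rules have the same three branches.
- **SAP 3.2.19**, after Table 9, gives three bullets tied to the third administration in the preceding cohort. Above 33% DLTs: "the activity for the next cohort will be reduced to a cumulative administered activity which did not lead to DLT occurrence with this frequency". The second branch reads "subjects in the next cohort will receive the same cumulative activity or less than in the preceding cohort". The third lets the next cohort go up to 7.4 GBq per administration.

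The 3.2.19 bullets are introduced by "This cumulative activity in the cohort being evaluated will be determined by the following DLT rules". SAP 3.2.17 gives the DRB two tasks, namely to "decide whether to proceed with the enrolment of the next cohort dose level and the cumulative radioactivity within a cohort".

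Table 9 holds the start decision for each cohort. The DRB-F row, on Cohort 2, is timed at "Cohort 1 EOC-3 and Cohort 3 EOC-3 and Cohort 5 EOC-1" (EOC = end of cycle). Its decision cell says to start Cohort 2 if modelling favours 300 µg and DLTs exceed 33% in both Cohort 1 and Cohort 5.

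**The concern.** A cohort that is not opened has no activity to reduce, so the two actions cannot both be followed for a cohort still closed. Nothing in the SAP ranks one list above the other. These rules are the main safety control on escalation in Part B and should give the DRB one answer. At stake is whether further subjects are treated in a new cohort after a toxic one, and at what activity.

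**Working it through.** No sample size or power figure is involved. The check covers the trigger, the branches and the timing.

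**1. Is the trigger the same?** SAP 3.2.19 glosses more than 33% as more than one of three to five subjects. Dividing DLT subjects by cohort size:
- Two subjects: 2/3 = 66.7%, 2/4 = 50.0%, 2/5 = 40.0%, all above the threshold.
- One subject: 1/3 = 33.3%, 1/4 = 25.0%, 1/5 = 20.0%. Taken literally 33.3% exceeds 33%, but the gloss settles that one of three does not count.

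Both lists therefore fire at two or more DLT subjects in a cohort of three to five. Cohort 6 enrols eight to ten, where the percentage is first exceeded at 3/8 = 37.5% or 4/10 = 40.0%.

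**2. Which branches differ?** The second branch is nearly identical in the two lists. The third lets the next cohort proceed in both. Only the branch above 33% differs in kind: no cohort against a cohort at lower activity.

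**3. When can both rules apply?** Once the next cohort is open, a bar on opening it is moot and only the reduction has content. The clash needs a next cohort unopened at the preceding cohort's EOC-3. Cohort 4 to Cohort 5 is not such a case: DRB-C decides at Cohort 4 EOC-1, and the Synopsis opens Cohort 5 after one cycle of Cohort 4. There the reduction bullet does useful work.

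**4. Which Table 9 rows use EOC-3 data to decide on an unopened cohort?** Three, all concerning optional cohorts:
- **DRB-F, Cohort 2** (Cohort 1 EOC-3, Cohort 3 EOC-3, Cohort 5 EOC-1). Taking Cohort 1 as the preceding cohort is natural: same 300 µg mass, and the second and third 3.2.19 bullets assume 6 GBq before 7.4 GBq. If Cohort 2 opened earlier, as the Synopsis condition on two completed Cohort 1 cycles could allow, the clash would not arise.
- **DRB-D, Cohort 7** (Cohort 6 EOC-3, Cohort 4 EOC-1) and **DRB-E, Cohort 8** (Cohort 6 EOC-3, Cohort 5 EOC-1). Both refuse the cohort at more than 33% DLTs in Cohort 6 Cycle 2. If Cohort 6 is the preceding cohort, the 3.2.19 bullet would only lower the activity. If Cohort 4, 5 or 7 is meant, these rows do not show a clash. Both rows also expressly allow a start when DLTs lie between 33% and 67% in Cohort 4 (DRB-D) or Cohort 5 (DRB-E) and modelling suggests the higher mass is safer.

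**5. What follows for Cohort 2 after a toxic Cohort 1?** Cohort 1 cumulative activity is 3 × 6.0 = 18.0 GBq. Cohort 2 as planned is 3 × 7.4 = 22.2 GBq.
- **SAP 3.2.18:** 0 subjects in Cohort 2. Protocol 3.8 separately lets the DRB agree to three further subjects one dose level down after a closure.
- **SAP 3.2.19:** three to five subjects below 18.0 GBq, since 18.0 GBq is the activity that proved toxic. No reduced level is named.
- **DRB-F as written**, if Cohort 5 also exceeds 33% and 300 µg is optimal: Cohort 2 starts, at 22.2 GBq unless another rule lowers it.

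The Cohort 1 inequality in DRB-F looks reversed. It makes toxicity at 18.0 GBq a condition for giving 22.2 GBq at the same mass, whereas the Synopsis opens Cohort 2 only if no safety signal is seen in Cohort 1.

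**The case against.** The best defence is that the lists serve the two DRB tasks in SAP 3.2.17: Table 9 decides on opening, and the 3.2.19 bullets then set activity. Their lead-in speaks of cumulative activity, and 3.2.18 is not absolute in any case. DRB-B waits for three more subjects between 33% and 67%, and DRB-D and DRB-E can open cohorts in that range. On the literal DRB-F text, Cohort 2 opens and the bullet lowers its activity, so those two fit together.

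Part of this stands. The Table 9 exceptions are real and any repair must respect them. The bullet is also needed for open cohorts and should not be deleted. But the two-task reading removes the clash only if the bullet is limited to cohorts already open or opened by Table 9, and the text does not say so. Pairing DRB-F with the bullet merely moves the conflict to 3.2.18 and Protocol 3.8.

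A reader might infer that the SAP departs from the Protocol. That cannot be concluded: Protocol 3.8 refers DRB detail to Appendix 3 and a charter, neither of which was available, and they may carry the same bullet. A reader might also infer that the plan means to escalate after toxicity. On the branch above 33%, neither 3.2.18 nor 3.2.19 escalates, and the DRB-F sign is more plausibly an error than an intention.

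**Conclusion.** The text is wrong as written, and the consequence is minor. For one trigger the SAP gives two incompatible actions whenever the next cohort is unopened at the preceding cohort's EOC-3. For Cohort 2 the DRB-F row adds a third: bar, reduce or start. The possible range is 0 subjects, three to five below 18.0 GBq, or three to five at 22.2 GBq. Protocol 3.1.3 puts the number at three per remaining cohort if all cohorts are used.

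This rests on Cohort 1 preceding Cohort 2. For Cohorts 7 and 8 the clash is conditional on Cohort 6 being the preceding cohort. It would be too strong to say that every escalation step is affected, since Cohort 4 to Cohort 5 is not. It would be too narrow to say that only Cohort 2 is. The documents give no DLT rate and no chance of reaching these decisions, so no probability is offered.

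Cohorts 2, 7 and 8 are optional. Cohort 2 is also dropped if the optimal mass exceeds 300 µg. The DRB core team makes all final decisions, and no endpoint, analysis set or estimate changes.

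**What to change.** 1. In the first bullet after Table 9 in SAP 3.2.19, state that a next cohort not yet open stays closed, except where a Table 9 row (DRB-D, DRB-E) expressly allows a start at more than 33% and less than 67% DLTs. State that the activity reduction applies to a cohort already open, or opened under such a row. Keep the bullet, which protects cohorts such as Cohort 5.
2. Correct the DRB-F row so that Cohort 2 starts only if DLTs are at or below 33% in Cohorts 1 and 5, in line with Protocol 3.8 and the Synopsis no-safety-signal condition.
3. Define *preceding cohort* for each Table 9 row.
4. Carry the same wording into Protocol Appendix 3 and the DRB charter if they hold the bullet or the table.

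The cost is a clause, one corrected row and a short definition in the SAP, plus matching edits in the other two documents if needed. No analysis has to be reprogrammed.

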3.2.20 Covariates and analysis of subgroups

No adjustment on covariate and no subgroups analysis are planned to be performed.

4 COMPUTER SYSTEMS, SOFTWARE AND VALIDATION OF PROGRAMS

4.1 Hardware

The statistical analysis will be performed using Windows 7 or higher version.

4.2 Software

All tables, listings and figures will be produced, and statistical analysis performed using SAS® version 9.2 or higher version. All output will be in Microsoft Word Format.

4.3 Validation programs

SAS® programs are developed to produce clinical study output such as analysis data sets, summary tables, data listings, figures or statistical analyses. Covance SOP **CCI**

CCI provides an overview of the development of such SAS® programs and describes the quality control procedures that must be performed for all SAS® programs and outputs. Quality control (QC) is defined here as the operational techniques and activities undertaken to verify that the SAS® programs produce the proper clinical study output by checking for their logic, efficiency and commenting, and by inspection of the produced outputs.

CCI will be prepared to document the methods of validation.

Copies of the internal QC forms produced for the validation process and the Covance’s sign-off forms will be provided to the sponsor to support the validation.

4.4 Restitution of the programs

All programs (including Macros and analysis datasets) producing the tables, listings and statistical output along with associated logs should be given to the sponsor when the tables, listings, figures and statistical analysis has been finalised.

5 CHANGES FROM PROTOCOL

Dosimetry sections:

Cumulative absorbed dose to the lesions (Gy) has been added as dosimetry endpoint.

AE section:

AESI definition was updated to “any TEAE related to ¹⁷⁷Lu-OPS201 which occurs the day of ¹⁷⁷Lu-OPS201 administration (same date as ¹⁷⁷Lu-OPS201 administration and at any cycle). “

7 APPENDICES

7.1 Appendix 1: Derived Data

The following derived data will be calculated and included in the listings:

(1) BMI

BMI (kg/m²) will be derived as $\text{Weight (kg)} / [\text{Height(cm)} / 100]^2$ and rounded to the nearest decimal. Underweight is defined as BMI < 18.5, normal as between 18.5 and 25, and overweight as ≥ 25 .

(2) Body Surface Area

Body Surface Area (m²) will be derived with the Mosteller formula as $(\text{Weight (kg)} * \text{Height(cm)} / 3600)^{1/2}$ and rounded to the nearest decimal.

(3) Changes from baseline

Changes from baseline will be calculated as a difference from baseline (e.g. assessment at the visit – assessment at baseline).

(4) Adverse event duration

If the start and end dates of the adverse event are identical then “<1” day will be presented with the duration in hh:mm recorded in the eCRF if it is available. If times are available, the duration will be calculated as (end date/time – start date/time) and presented in days hh:mm. If at least one time is missing and if the duration is greater than 24 hours then it will be calculated as (end date - start date)+1 and presented in days. If the recorded end date is CONT. (for continuing), the end date will be listed as “ongoing” and the duration will be approximated as “ \geq (last attended visit date – start date)+1” day(s). If the start date or the end date are partial the duration will be presented as a superior inequality “ \geq xx” day(s) [i.e.: ≥ 2 where start date=31JAN2004 and end date=FEB2004 or start date=JAN2004 and end date=01FEB2004].

(5) Time since last dose for adverse event

If the start date of the adverse event is identical to the date of last administration, then “<1” day will be presented with the time to onset in hh:mm recorded in the eCRF if it is available. If

times are available, the time will be calculated as (start date/time – last administration date/time) and presented in days hh:mm. If at least one time is missing and if the time to onset is greater than 24 hours then it will be calculated as (start date - last administration date)+1 and presented in days. If the start date and the associated information do not allow to state about the last dose received (partial start date or start at administration day without knowing if it started before or after the drug intake), all the possible time since last dose will be presented [i.e.: if a subject received a daily administration and reported an AE at second administration day but without indication about before or after the drug intake the time since last dose will be as “2 / <1”]. If the start date is partial, the time since last dose will be presented as an superior inequality (i.e.: for an AE started in FEB2004 after the only administration performed on 31JAN2004, the time since last dose will be as “≥2” days). If the start date is missing the time since last dose will not be presented although the AE will be assigned to each dose received before its end date.

(6) Days since last dose for study drug administration or discontinued subject

The days since last dose for study drug administration will be calculated as (drug administration date/time - previous administration date/time)+1 and presented in days hh:mm. The days since last dose for discontinued subject will be calculated as (discontinued date - last administration date)+1 and presented in days.

(7) Time since initial diagnosis (months) will be calculated as (screening date - date of initial diagnosis + 1)/30.4375

(8) Time since histologically confirmed NET diagnosis (months) will be calculated as (screening date - date of histologically confirmed NET diagnosis + 1)/30.4375

(9) Time since scan of positive somatostatin receptor documentation (months) will be calculated as (screening date - date of scan of positive somatostatin receptor documentation + 1)/30.4375

(10) Time since last relapse/ time since last previous surgery for NET (months) will be calculated as (screening date - date of last relapse/surgery + 1)/30.4375

(11) Study exposure

Study exposure in days will be calculated as (last visit attended - first inform consent signed date) + 1.

(12) Duration of Study Drug Exposure

Duration (days) = (last dose or infusion date - first dose or infusion date +1)

(13) Delay in injection

A delay in injection is defined as an injection performed more than one day after the scheduled injection date.

The number of days of delay will be positive and calculated as the difference between the actual injection date and the scheduled injection date.

(14) **Injection performed in anticipation**

An injection performed in anticipation is defined by an injection performed more than 1 day in advance compared to the scheduled date.

The number of days of anticipated injections will be positive and calculated as the difference between the scheduled injection date and the actual injection date.

(15) **Concomitant therapy duration**

If times are available, the duration of concomitant treatments/physiotherapy etc. will be calculated as (end date/time - start date/time). If at least one time is missing, the duration of concomitant treatments will be calculated as (end date - start date) +1. If the recorded end date is CONT. (for continuing) then the end date will be listed as “ongoing” and the duration will be approximated as “≥(last attended visit date – start date)+1” day(s). If the start date or the end date are partial, the duration will be presented as an inequality “≥xx” day(s) [i.e.: ≥2 where start date=31JAN2004 and end date=FEB2004 or start date=JAN2004 and end date=01FEB2004] but if both are partial or one is missing the duration will not be presented.

(16) **Study day**

Study day will be defined as ‘-1’ for the day prior to treatment and as ‘1’ for the day of treatment (i.e. day 0 does not exist).

(17) **For quantitative statistics of biological values, a standardization method will be used in order to take into account the differences between the reference ranges of the different laboratories:**

In a general way, standardised values will be assessed using the following formula:

$$X_{St.} = X_{LRef} + (X_{URef} - X_{LRef}) \frac{X - X_L}{X_U - X_L}$$

where X = measured value,

XL = lower limit value for the laboratory of the measured value,

XU = upper limit value for the laboratory of the measured value,

XLRef. = lower limit value for the laboratory chosen as a reference,

XURef. = upper limit value for the laboratory chosen as a reference,

If a standardised value is negative it will be replaced by 0.

There is no missing value for any reference value.

(18) **A nadir** for a subject is defined as the lowest laboratory value during the whole treatment period (all cycles combined) among all infusions for that subject and a nadir for a cycle is defined as the lowest laboratory value in that cycle. The day to nadir in a cycle is the number of days between the nadir and the first date of study medication intake of that cycle.

(19) **Whole body absorbed dose**

$$\text{AbsorbedDose_WholeBody [Gy]} = \text{AUC}_{\text{WholeBody}} [\text{Bq.s}] \times E_{\text{beta}} / \text{Weight}_{\text{WholeBody}} [\text{kg}]$$

With $E_{\text{beta}} = 2.3664 \times 10^{-14} \text{ J.Bq}^{-1} \cdot \text{s}^{-1}$.

(20) Whole body specific absorbed dose

$$\text{Specific_AbsorbedDose_WholeBody [Gy/GBq]} = \frac{\text{AbsorbedDose_WholeBody [Gy]}}{\text{Radioactivity_administered [GBq]}}$$

(21) Amount excreted (Ae) for cold PK urine sample

$$\text{Ae [ng]} = \text{ConcentrationOPS201_urine (ng/mL)} \times \text{volume urine collected (mL)}$$

CCI

CCI

CCI

CCI

CCI

CCI

CCI

CCI

CCI

CCI

CCI

CCI

CCI
